### **Duration of nebulization**

Upon review of the tables, figures and listings produced at the end of the study, an exploratory analysis may be performed to evaluate the effect of duration of nebulization on primary and/or secondary outcomes if deemed appropriate following review of the summary data and nebulization times. The decision to perform this analysis will be made by the Sponsor. If the decision is made not to proceed, this section of the SAP will not be applicable and the outputs described herein will not be presented.

## 9. PHARMACODYNAMICS

### 9.1. Overview of Pharmacodynamics Analyses

The primary analysis of the primary pharmacodynamics endpoint will be performed on both the FAS (primary) and the PP (supportive) population. The secondary analysis of the primary pharmacodynamics endpoint will be performed on the FAS. The analysis of the secondary pharmacodynamics endpoint will be performed on the FAS.

The primary endpoint is the change from baseline (Day 1) at Day 21 (Week 3) in trough FEV1 response at approximately 24 hours after the last dose (average of 23 hours 15 minutes and 23 hours 45 minutes post-dose measurements), in comparison with GSP304 placebo.

Table 11 provides an overview of the planned primary pharmacodynamics analyses.

**Table 11: Overview of Pharmacodynamics Analyses**

	Stats Analysis		Summary		Individual
	T	F	T	F	L
Primary Endpoint - FAS					
Change from baseline (Day 1) at Day 21 (Week 3) in trough FEV 1 response at approximately 24 hours after the last dose (average of 23 hours 15 minutes and 23 hours 45 minutes post-dose measurements)	Y 		Y	Y	
Perform on PP	Y 		Y	Y	
Sensitivity Analysis - Pattern-Mixture model	Y				
Sensitivity Analysis - Tipping Point approach	Y				
Exploratory Analysis	Y	Y			
Secondary Endpoints - FAS					
Change from baseline in Peak FEV 1 within 12 hours post-dose on Day 1 and Day 21	Y 		Y	Y	
Change from baseline (Day 1) at Day 21 (Week 3) in trough FVC response at approximately 24 hours after the last dose (average of 23 hours 15 minutes and 23 hours 45 minutes post-dose measurements)	Y 		Y	Y	
Change from baseline in time-normalized area under the curve for FEV 1 measured over 12 hours on Day 1 and Day 21	Y 		Y	Y	
Time to onset of response, defined as at least 12% and 200 mL increase in FEV 1 within 12 hours of dosing on Day 1			Y	Y	
Time to achieving steady state as measured by FEV 1 trough assessments			Y	Y	
Time to achieving steady state as measured by FVC trough assessments			Y	Y	

NOTES :

- T = Table, F = Figure, L = Listing, Y = Yes display generated.
- Stats Analysis = Represents TF related to any formal statistical analyses (ie modeling) conducted.

- 
- Summary = Represents TF related to summaries (ie descriptive statistics) of the baseline, post-treatment and change from baseline for the primary pharmacodynamics analyses method.
  - Individual = Represents L related to any displays of individual subject observed raw data.
  - [1]: MMRM method applied

## **9.2. General Considerations**

All tests will be 2-sided and at 5% level of significance unless otherwise stated.

In addition to the analyses described below, all endpoints will be summarized over time, by treatment, as appropriate.

All endpoints will also be listed by treatment and subject. The interpretation of results from statistical tests will be based on the FAS. The PP population will be used to assess the robustness of the results from the statistical tests based on the FAS. Unless otherwise stated, ‘treatment’ refers to treatment group as randomized, rather than based on the actual treatment received.

## **9.3. Testing Statistical Assumptions Including Comparability at Baseline**

All baseline data will be summarized by treatment group using descriptive statistics. No formal hypothesis testing will be conducted. Differences may occur by chance. If there are any clinically meaningful differences identified, analyses may be adjusted to account for these imbalances through inclusion of additional covariates in the statistical models.

The PD endpoints (FEV1, FVC) are assumed to be normally distributed and will be analyzed under this assumption. The assumptions of normality and constant variance will be verified using diagnostic plots (normal quantile plots and scatter plots of residuals by treatment group). If assumptions are violated, either an appropriate transformation will be used or data will be analyzed using non-parametric methods. The methods used will be documented in the clinical study report.

## **9.4. Statement of the Null and Alternate Hypotheses**

A significance test will be made for the primary pharmacodynamics endpoint in order to assess for superiority of GSP304 versus GSP304 placebo. Demonstration of superiority for this treatment comparison will be based on a hypothesis testing approach, whereby the null hypothesis is that there is no difference between treatment groups and the alternative hypothesis is that there is a difference between the treatment groups.

A 2-sided 5% risk associated with incorrectly rejecting the null hypothesis (significance level) is considered acceptable for this study.

## **9.5. Multiple Comparisons and Multiplicity**

As this is a phase 2 study, no adjustments for multiplicity are planned. The nominal p-values of all hypothesis tests will not be adjusted for multiplicity.

## **9.6. Analysis of the Primary Pharmacodynamics Endpoint**

### **9.6.1. Primary Pharmacodynamics Analysis**

The primary endpoint, change from baseline (Day 1) at Day 21 (Week 3) in trough FEV1 response at approximately 24 hours after the last dose (average of 23 hours 15 minutes and 23 hours 45 minutes post-dose measurements) will be analyzed using a mixed-effect repeated measures (MMRM) model. This model will assume that any missing data is Missing at Random (MAR). The model will include trough data from all visits (Days 1, 6, 13, 20 and Day 21), and fixed terms for treatment, visit, center, baseline, treatment by visit and baseline by visit interactions. If an interaction term is significant, further ad-hoc analysis may be conducted. Subject will be included as a random term to account for the correlation between repeated measurements within a subject, and unstructured covariance structure will be used. If the model fails to converge, alternative structures (VC, AR1, TOEP1, and CS) or removing terms will be investigated. The covariance structure that provides the best fit (as determined by the smallest AIC value) will be used.

The statements of a SAS® PROC MIXED analysis would be:

```
PROC MIXED data=dataset method= REML;  
  CLASS subject treatment center visit;  
  MODEL change = treatment center visit baseline treatment*visit  baseline*visit /s ddfm=kr;  
  REPEATED visit/subject=subject type=UN;  
  LSMEANS treatment*visit/at mean cl diff e;  
RUN;
```

The adjusted means for each treatment and the estimated treatment differences for the treatment comparisons will be presented together with 95% confidence intervals, along with p-values for the treatment comparisons. The adjusted means and estimated treatment differences for the treatment comparisons (each GSP304 vs placebo, total GSP304 vs placebo, and Spiriva vs placebo) will also be plotted, with corresponding 95% confidence intervals.

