## **9.7. Analysis of the Secondary Pharmacodynamics Endpoints**

The secondary endpoints are:

- Change from baseline in peak FEV1 within 12 hours post-dose on Day 1 and 21
- Change from baseline (Day 1) at Day 21 (Week 3) in trough FVC response at approximately 24 hours after the last dose (average of 23 hours 15 minutes and 23 hours 45 minutes post-dose measurements)
- Change from baseline in time-normalized area under the curve for FEV1 measured over 12 hours on Day 1 and 21
- Time to onset of response, defined as at least 12% and 200 mL increase in FEV1 within 12 hours of dosing on Day 1
- Time to achieving steady state as measured by FEV1 trough assessments
- Time to achieving steady state as measured by FVC trough assessments

The change from baseline for the secondary pharmacodynamics endpoint of change from baseline (Day 1) at Day 21 (Week 3) in trough FVC response at approximately 24 hours after the last dose (average of 23 hours 15 minutes and 23 hours 45 minutes post-dose measurements) will be analysed using the same model as described above for the analysis of the primary endpoint.

The change from baseline for the secondary pharmacodynamics endpoints of; Change from baseline in peak FEV1 within 12 hours post-dose on Day 1 and 21 and change from baseline in time-normalized area under the curve for FEV1 measured over 12 hours on Day 1 and 21 will be analyzed using a mixed-effect repeated measures (MMRM) model. This model will assume that any missing data is Missing at Random (MAR). The model will include data from Day 1 and Day 21 and fixed terms for treatment, visit, center, baseline, treatment by visit and baseline by visit interactions. If an interaction term is significant, further ad-hoc analysis may be conducted. Subject will be included as a random term to account for the correlation between repeated measurements within a subject, and unstructured covariance structure will be used. If the model fails to converge, alternative structures (CS) or removing terms will be investigated. The covariance structure that provides the best fit (as determined by the smallest AIC value) will be used. The adjusted means for each treatment and the estimated treatment differences for the

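### If the unstructured model fails to converge, every listed fallback for the primary MMRM forces one variance on all five visits, so the Day 21 test may run below or above 5%

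*SAP*

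**What the plan says.** For the primary endpoint, SAP section 9.6.1 states: "The model will include trough data from all visits (Days 1, 6, 13, 20 and Day 21". The planned structure is clear: "unstructured covariance structure will be used". In the code it enters only through "REPEATED visit/subject=subject type=UN", and the fixed effects are given as "MODEL change = treatment center visit baseline treatment*visit baseline*visit /s ddfm=kr". Standard errors are therefore model-based with Kenward-Roger degrees of freedom. There is no empirical option and no separate variance by group.

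The fallback opens with "If the model fails to converge" and continues "alternative structures (VC, AR1, TOEP1, and CS) or removing terms will be investigated". The section then adds: "The covariance structure that provides the best fit (as determined by the smallest AIC value) will be used".

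Section 9.7 models peak FEV1 and FEV1 AUC on two visits, Day 1 and Day 21. Its fallback is shorter: "alternative structures (CS) or removing terms will be investigated".

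Section 9.4 accepts a two-sided 5% risk of wrongly rejecting the null. Section 4.3.1 gives the only SD in the plan, 170 mL, with no value by visit and no within-subject correlation.

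**The concern.** Primary inference is on one visit, Day 21, so its standard error should reflect the Day 21 variance. In a REPEATED statement, VC, AR(1), Toeplitz and CS differ in how they model correlation, but each has a single variance parameter. Under any of them the Day 21 standard error uses a variance averaged over the five visits. If Day 21 is more variable than that average, the standard error is too small and the test rejects too often. If Day 21 is less variable, the test is conservative.

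AIC ranks only the candidates it is given, and here all of them share the restriction. The assumption check in section 9.3 would not reliably show the problem, because it plots residuals by treatment group and not by visit.

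A second gap is that the permission to remove terms is unrestricted. Without treatment-by-visit, the model would estimate an effect averaged over visits and not the Day 21 effect.

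**Working it through.** **Inputs from the SAP.** 28 evaluable per arm, 31 randomized per arm, five arms, 10% dropout, difference 150 mL, SD 170 mL, two-sided 5% (sections 4.3.1 and 9.4); five visits (section 9.6.1).

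**The plan's own figure.** A two-sample noncentral t calculation with 150 mL, 170 mL and 28 per arm gives power 0.900, so the stated 90% is reproduced. The SAP gives no error rate for a fallback fit.

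**What the structures assume.** As residual structures over five visits:
- UN: 5 × 6 / 2 = 15 parameters, with a separate variance at each visit.
- CS and AR(1): one variance and one correlation.
- VC: one variance, no correlation. TOEP1 is the same model if it means one-band Toeplitz. If full Toeplitz was meant, correlations are allowed but there is still one variance.

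**Closed form.** With complete data, let r be the Day 21 SD divided by the pooled SD, where pooled SD = √(mean of the five visit variances). The actual two-sided level is approximately 2 × [1 − Φ(1.96 / r)].
- A level of 7% needs r = 1.082 (variance ratio 1.17).
- A level of 9% needs r = 1.156 (variance ratio 1.34).

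Worked example with SD 150 mL on the first four visits and 170 mL on Day 21: mean variance = (4 × 22,500 + 28,900) / 5 = 23,780; pooled SD = 154.2; r = 170 / 154.2 = 1.102; 1.96 / 1.102 = 1.778; level = 7.5%.

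**Simulation under the null.** The SAP model was fitted by REML with 31 per arm, 10% monotone dropout, 8 centers (assumed) and 6,000 trials per scenario. True correlation was CS 0.6 or AR(1) 0.8, plus a time-decay pattern in four of the SD patterns. Kenward-Roger degrees of freedom were approximated. Every by-visit SD pattern below is an assumption; Day 21 is held at 170 mL.

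| SD by visit, mL (Days 1, 6, 13, 20, 21) | r | Closed form | Simulated, AIC-chosen fallback |
|---|---|---|---|
| 190, 180, 175, 170, 170 | 0.960 | 4.1% | 3.5-4.0% |
| 170 throughout | 1.000 | 5.0% | 4.7-5.1% |
| 140, then 170 | 1.034 | 5.8% | 5.9-6.6% |
| 145, 155, 162, 170, 170 | 1.058 | 6.4% | 6.5-6.9% |
| 150 × 4, then 170 | 1.102 | 7.5% | 6.6-7.5% |
| 130, 145, 158, 170, 170 | 1.094 | 7.3% | 7.3-8.3% |
| 110, 135, 155, 170, 170 | 1.135 | 8.4% | 8.7-9.1% |

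A Day 21 ANCOVA, which equals UN when Day 21 data are complete, gave 4.99%.

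**Which restriction drives it.** AIC chose the zero-correlation model in 0% of trials in every scenario. Forcing that model gave 5.3-5.8% with equal SDs and 8.2-9.6% in the two steepest rising patterns, so zero correlation adds less than one point in most cases. The common variance is the main cause.

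**Section 9.7.** With two visits, CS pools exactly the Day 1 and Day 21 variances. For assumed SDs of 140 and 170 mL: pooled SD = √((19,600 + 28,900) / 2) = 155.7, r = 1.092, level 7.3%. For 120 and 170 mL: pooled SD 147.1, r = 1.155, level 9.0%.

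**The case against.** The strongest reply is that the fallback may never be used. UN with 15 covariance parameters is fitted to about 140-155 subjects with 10% expected dropout, and nothing in the SAP suggests it will fail. This stands, and it is the main reason the point is minor.

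A reader might infer that the primary test will run at 7-9%. The SAP does not support that. It gives no SD by visit, and the level can equally be 5% or about 4%.

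A reader might also take the AIC sentence as a choice among all structures, UN included, and fear the same inflation there. That does not follow. With UN among the candidates and steeply rising SDs, simulation gave it the smallest AIC in about 96-100% of trials.

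The independence structures look like the worst entries in the list, but the AIC rule did not select them. The text also calls subject a random term. If that became a random intercept, VC would amount to CS.

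Losing treatment-by-visit is a gap in wording and not a stated intention. The planned least-squares means are by treatment and visit, and the technical summary puts primary inference on Day 21.

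Finally, this is a phase 2 trial with unadjusted nominal p-values (section 9.5), and the jump-to-reference analysis in section 9.6.2.1 uses ANCOVA on imputed data, which need not depend on the fallback covariance. That limits the consequence. It does not answer the fact that the prespecified fallback offers no option with a separate Day 21 variance.

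**Conclusion.** The point holds in a conditional form and is minor. If UN is abandoned, all four alternatives in section 9.6.1 impose equal variances over visits, and selection by AIC cannot undo that. The size rests on assumed by-visit SDs: about 5% with equal SDs, about 3.5-4% if they fall, and about 6-9%, up to about 10% in steep patterns, if the Day 21 SD is clearly above the pooled SD. The stated risk is 5%. The documents establish neither the direction of the error nor the chance that UN fails.

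**What to change.** In section 9.6.1, replace the list and the AIC choice with a fixed order: TOEPH, then ARH(1), then CSH. Use the first that converges, keeping Kenward-Roger degrees of freedom. If all three fail, analyze Day 21 by ANCOVA with treatment, center and baseline. State that center is the only term that may be removed, so that treatment-by-visit stays.

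In section 9.7, CSH would not serve. With two visits it has two variances and one correlation, which is UN in another parameterization. Replace the CS fallback with separate ANCOVAs for Day 1 and Day 21.

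This changes SAP wording only. The cost falls on a rarely used fallback: a few more covariance parameters (9 for TOEPH and 6 for ARH(1) or CSH over five visits, against 2 for CS or AR(1)), or, under the ANCOVA, the loss of information from earlier visits for subjects without a Day 21 value.

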### **9.6.2. Sensitivity Analyses of the Primary Pharmacodynamics Results**

Sensitivity analyses will be performed on the FAS only. Subjects with at least one post-baseline assessment will be used in modeling.

#### **9.6.2.1. Pattern-Mixture Model**

The Mixed-effect Model Repeated Measure (MMRM) model will be fitted when some of the response values are missing by assuming that they are missing at random (MAR). This will be done computationally using Restricted Maximum-Likelihood (REML). However, this

assumption is unverifiable. It is necessary to perform sensitivity analyses under different assumptions regarding missing data. When the MAR assumptions do not hold, the data are assumed to be Missing Not At Random (MNAR). One possible way forward is to model a separate distribution for each pattern of missingness. A sensitivity analysis for missing data will be conducted based on multiple imputation-based methods with a form of pattern-mixture model (PMM).

PMMs will be fitted based on multiple imputations method. In the multiple imputation approach, a model will be fitted to the incomplete data and a pseudo-independent sample drawn from the posterior distribution of parameters. Each member of the sample leads to a separate imputed dataset, in which the missing values will be replaced by values drawn randomly from their conditional distribution. This distribution is based on the observed data and the covariates for that subject using the imputation model and the sampled parameter values. Each dataset is then analyzed as if these were real data, leading to a series of estimates for a parameter. These are then combined to supply an overall estimate and standard error based on Rubin's classic rules (Rubin, 1987) for combining across imputations.

The primary endpoint will also be analyzed using a Jump to Reference (J2R) approach, that is, all the patterns have the same profile up to withdrawal (that estimated in the parameter estimation model), but after withdrawal the profile jumps to the estimated profile for the reference arm. This approach is a multiple imputation technique and works under the assumption that data is missing not at random (MNAR).

The J2R approach involves three distinct steps:

1. The missing data are filled in  $m$  times to generate  $m$  complete data sets ( $m$  will be selected to provide sufficiently stable and reproducible results).
  - In J2R method, all the patterns have the same profile up to withdrawal (that estimated in the parameter estimation model), but after withdrawal the profile jumps to the estimated profile for the reference arm. A new model is simulated from the posterior predictive distribution of the fitted model and missing values of the variable are imputed based on the new model.
  - The MNAR statement together with a MONOTON statement in PROC MI will be used. The variables that have missing values are imputed sequentially in each imputation. If the missing pattern is arbitrary, first the MCMC method will be used to partially impute data in order to obtain a monotone missing data pattern.
2. The missing data are filled in  $m$  times to generate  $m$  complete data sets. The  $m$  complete data sets are analyzed by using a procedure.
  - ANCOVA analysis for change from baseline in trough FEV1 is performed using PROC MIXED with LSMEANS statement.
3. Results of the ANCOVA analysis on  $m$  imputed datasets can be combined to derive an overall result. PROC MIANALYZE in SAS will be used to combine the results.

The adjusted means for each treatment and the estimated treatment differences for the treatment comparisons will be presented together with 95% confidence intervals for the differences and p-values for the treatment comparisons.

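### The sensitivity analysis labelled jump-to-reference is specified with sequential monotone imputation, which as usually run is copy-reference and applies only part of the intended penalty

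*SAP*

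**What the plan says.** Section 9.6.2.1 of the SAP sets up multiple imputation as a check on the missing-at-random (MAR) assumption of the primary repeated-measures model. It describes J2R twice, in the standard way: a subject follows the estimated profile up to withdrawal, and "after withdrawal the profile jumps to the estimated profile for the reference arm". The section does not say which arm is the reference.

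The first of the three J2R steps then fixes the implementation. "The MNAR statement together with a MONOTON statement in PROC MI will be used" (the second statement is evidently MONOTONE), and "The variables that have missing values are imputed sequentially in each imputation". Arbitrary missingness patterns are first made monotone by an MCMC step. The section does not list the predictors, say which subjects the imputation model is fitted to, or describe subtracting the own-arm mean from a subject's history. It gives no code, although sections 8.4, 8.5 and 9.6.1 do.

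Section 9.6.2 adds that "Subjects with at least one post-baseline assessment will be used in modeling". The shell of Table 14.2.1.5 prints two rows: multiple imputation under MAR, and multiple imputation under missing not at random (MNAR), labelled J2R.

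**The concern.** Under J2R, the mean benefit that a withdrawn active-arm subject keeps is zero. This works because only the subject's residual from the own-arm mean is carried past withdrawal. A sequential regression works on the raw earlier values, and in an active-arm subject those values contain the drug effect. If the regression is fitted in placebo, the subject is treated as a placebo subject who happened to do well, and part of the benefit persists. That is copy-reference, a milder assumption. If the regression is not confined to placebo, nothing in it refers to the reference arm.

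What is at stake is the meaning of a labelled result. Agreement between the two rows of Table 14.2.1.5 would be read as robustness to J2R, when it would partly come from the procedure itself.

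**Working it through.** **Inputs from the SAP.** Effect 150 mL, SD 170 mL, two-sided 5%, 28 per arm for 90% power, 10% dropout, 31 per arm randomized (section 4.3.1). Five trough visits, Days 1, 6, 13, 20 and 21 (section 9.6.1), so a subject missing Day 21 has k = 1 to 4 observed troughs.

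**The plan's own figure.** Noncentral t power at 28 per arm is 90.0%, as stated. 140/0.9 = 155.6, consistent with 155 up to rounding (31 × 0.9 = 27.9 per arm).

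**Assumed, because the SAP is silent.** Earlier visits as predictors, with the model fitted in placebo. Correlation ρ from 0.3 to 0.9, either exchangeable (CS) or AR(1) by visit order. Dropout spread evenly over the four possible last visits. Effect either flat at 150 mL or rising 90, 130, 150, 150, 150 mL.

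**Imputed Day 21 mean for an active-arm dropout.** Let B be the coefficients of Day 21 on the observed visits.
- J2R: μ_ref + B(y_obs − μ_own). The second term averages zero, so no effect is retained.
- Sequential, fitted in placebo: μ_ref + B(y_obs − μ_ref). The average excess over placebo is Bδ_obs, where δ_obs is the effect at the observed visits.

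**Estimate at 10% dropout.** 0.9 × 150 + 0.1 × (retained effect). J2R gives 135 mL, a 15 mL penalty.

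For CS with a flat effect, the retained fraction is kρ/(1 + (k−1)ρ). At ρ = 0.5 this is 0.50, 0.67, 0.75 and 0.80 for k = 1 to 4, with mean 0.68, so the estimate is 135 + 0.1 × 0.68 × 150 = 145.2 mL. For AR(1) with a flat effect, the fraction is ρ^(5−k).

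| Correlation | Flat: mL (penalty lost) | Rising: mL (penalty lost) |
|---|---|---|
| CS 0.3 | 142.3 (49%) | 140.7 (38%) |
| CS 0.5 | 145.2 (68%) | 142.9 (52%) |
| CS 0.7 | 147.4 (83%) | 144.5 (63%) |
| CS 0.9 | 149.2 (95%) | 145.8 (72%) |
| AR(1) 0.3 | 136.6 (11%) | 136.6 (10%) |
| AR(1) 0.5 | 138.5 (23%) | 138.4 (22%) |
| AR(1) 0.7 | 141.6 (44%) | 141.1 (41%) |
| AR(1) 0.8 | 143.9 (59%) | 143.0 (53%) |
| AR(1) 0.9 | 146.6 (77%) | 145.3 (68%) |

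**Simulation check.** Large-sample multiple imputation under CS gave 134–138 mL for J2R. The sequential method gave 141–150 mL (flat) and 140–146 mL (rising). Monte Carlo standard error was about 2 mL, consistent with the formulas.

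**No placebo restriction.** With treatment in the model, or with arms fitted separately, a dropout is imputed around the own-arm mean and the estimate is 0.9 × 150 + 0.1 × 150 = 150 mL, the MAR answer.

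**Scale.** The shift from J2R runs from 136.6 − 135 = 1.6 mL to 149.2 − 135 = 14.2 mL. The standard error of the difference is 170 × √(2/31) ≈ 43 mL, and 10% of 31 is about 3 dropouts per arm.

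**The case against.** The strongest reply is that the SAP states the right target twice and merely leaves the imputation model open. A model with baseline as its only predictor would give the J2R mean. The sentence that most suggests carrying history forward, "This distribution is based on the observed data and the covariates for that subject using the imputation model", belongs to the general multiple-imputation paragraph. It also fits true J2R, which conditions on history through residuals. This stands in part: a reader might infer that the SAP has fixed copy-reference, but it has not written the predictors or the fitting subset. What remains is that the procedure it does name supplies no step that produces the jump, and both natural ways of running it are milder than the label.

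A reader might also infer that most of the penalty is always lost, or that the result would nearly reproduce MAR. The document does not support either. It states no within-subject correlation and no early effect, and over the assumed range the loss runs from about 10% to 95%. Under AR(1) it exceeds half only from about ρ = 0.8.

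Nor is J2R the only MNAR check. The tipping-point analysis in section 9.6.2.2 considers active dropouts doing worse than placebo. Its first grid stops at −80 mL, which removes 0.1 × 80 = 8 mL at 10% dropout, but it is to be extended if no tipping point is found. A −150 mL shift on active alone would reproduce the full 15 mL penalty.

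**Conclusion.** The concern holds in a limited form. The procedure named in section 9.6.2.1 does not by itself deliver the J2R profile defined there. Fitted in placebo with earlier visits as predictors, it is copy-reference and gives about 137 to 149 mL where J2R gives 135 mL. Part of the penalty is lost, and more than half under exchangeable correlation of about 0.5 or more for both effect shapes. These figures rest on the planned effect and dropout and on correlations and dropout timing that the SAP does not state.

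With so few dropouts and a standard error near 43 mL, this is unlikely to reverse the trial's conclusion. The fault lies in the label: the J2R row of Table 14.2.1.5 would claim more robustness than it tests. It should be corrected, but it does not threaten the primary analysis.

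**What to change.** Before database lock, amend section 9.6.2.1 to name GSP304 placebo as the reference arm. This is worth stating because the SAP's Technical Summary Report lists Spiriva under its reference-therapy heading. Then do one of the following:

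- **Specify J2R from the joint multivariate normal model.** Use the own-arm mean before withdrawal, the placebo mean after it, and imputed mean μ_ref + B × (observed history − own-arm mean). Regressing on own-arm-centred history is equivalent.
- **Keep the stated procedure under its proper name.** Relabel it copy-reference in the text and in Table 14.2.1.5, state the placebo-only fit and the predictors, and add a true J2R row beside it.

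The cost is modest programming, a few lines of wording, and a sensitivity estimate that may come out slightly less favourable.
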